8.3. Exploratory Efficacy Analysis

No formal statistical testing will be performed on exploratory endpoints.

9. Safety and Tolerability Analysis

Safety will be evaluated from reported AEs, changes in clinical laboratory values, changes in vital signs, and physical examinations of the affected areas.

[figure not shown]
All safety analyses will be performed on the Safety population (as defined in Section 5).

9.1. Adverse Events

Missing and partially missing start dates will be imputed for the purpose of analysis as described in Section 6.1.8.

All adverse events (AEs), treatment emergent adverse events (TEAEs), and serious adverse events (SAEs) will be coded using the MedDRA v. 27.1. Treatment Emergent AEs are defined in Section 6.1.7.1.

The number and percent of subjects reporting treatment emergent AEs, grouped by MedDRA SOC and PT, will be tabulated. In the case of multiple occurrences of the same TEAE within the same subject, each subject will only be counted once for each PT.

A summary table will be created summarizing the number and percent of subjects with the following:

- At least one TEAE
- At least one possibly related TEAE
- At least one serious TEAE
- At least one serious TEAE possibly related to Study Drug
- At least one TEAE leading to permanent treatment discontinuation
- At least one TEAE leading to Death
- At least one TEAE by maximum severity

In addition, the following TEAE data will be summarized for each MedDRA SOC and PT:

- Incidence of overall TEAEs by SOC and PT
- Incidence of TEAEs by SOC, PT, and Severity
- Incidence of Severe TEAE by SOC and PT
- Incidence of TEAEs by SOC, PT, and Relationship
- Incidence of Related TEAEs by SOC and PT
- Incidence of Serious TEAEs by SOC and PT
- Incidence of TEAEs leading to Study Discontinuation

In the summaries showing severity and relationship to study medication the event with the maximum severity (Life Threatening>Severe>Moderate>Mild) or relationship (Related/Not Related) will be reported. If a particular event is missing the severity and/or relationship, then the strongest possible severity or relationship will be assumed for analysis (severity = severe, relationship = related).

In the AE data listings, all AEs will be displayed. AEs that are not treatment-emergent will be flagged. A listing of all AE data sorted by subject, including verbatim term, MedDRA SOC and PT, and all other information from the AE eCRF will be generated.

9.1.1. Adverse Events Leading to Withdrawal

[figure not shown]
A summary of incidence rates (frequencies and percentages) of TEAEs leading to withdrawal of study drug, by treatment group, SOC, and preferred term will be prepared for the Safety Population. No inferential statistical tests will be performed.

A data listing of AEs leading to withdrawal of study drug will also be provided, displaying details of the event(s) captured on the CRF.

9.1.2. Deaths and Serious Adverse Events

Any deaths that occur during the study will be listed.

Serious adverse events will be listed as well as tabulated by SOC and PT.

9.2. Clinical Laboratory Evaluations

[figure not shown]
Laboratory test results will be summarized descriptively by time point as both observed values and change from baseline values.

The number of subjects with clinical laboratory values below, within, or above the normal range by time point and in relation to baseline will be tabulated for each clinical laboratory analyte by treatment group (shift table).

Central Labs' normal ranges are provided from the Lab Vendor Q2 within the data transfer. Any local labs performed will utilize the local lab ranges input from the site into the EDC.

Lab Units will be standardized and displayed as follows:

Analyte Name	Unit
ALT	U/L
Albumin	g/L
Alkaline Phosphatase	U/L
AST	IU/L
Basophils	10^9/L
Basophils/Leukocytes	%
Bicarbonate	mmol/L
Direct Bilirubin	μmol/L
Total Bilirubin	μmol/L
Blood Urea Nitrogen	mmol/L
Calcium	mmol/L
Chloride	mmol/L
HCG	Positive/Negative
Creatinine	μmol/L
Eosinophils	10^9/L
Eosinophils/Leukocytes	%
Ery. Mean Corpuscular Volume	fL
Erythrocytes (RBC)	10^12/L
Erythrocytes Distribution Width (RDW)	%
FSH	IU/L
Glucose	mmol/L
HCT	Fraction of 1
HGB	g/L
HIV Screening	Reactive/Non-Reactive
Lactate Dehydrogenase	IU/L
Leukocytes (WBC)	10^9/L
Lymphocytes	10^9/L
Lymphocytes/Leukocytes	%
Mean Platelet Volume	fL

Monocytes	10^9/L
Monocytes/Leukocytes	%
Neutrophils	10^9/L
Neutrophils/Leukocytes	%
Phosphate	mmol/L
Platelets	10^9/L
Potassium	mmol/L
Protein	g/L
Sodium	mmol/L

Descriptive summaries of observed values and change from baseline will be presented for continuous hematology and chemistry for overall subjects at each study visit.

Laboratory values that are outside the normal range will be presented via a shift table and also be flagged in the data listings and presented with the corresponding normal ranges.

Serology tests including urinalysis, pregnancy, and HIV test results will be listed.

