A comprehensive analysis of potential systemic safety concerns with oral ruxolitinib as well as additional events of interest for oral JAK inhibitors that have not been observed with oral ruxolitinib was performed in the Phase 3 studies. Events of interest included cytopenias, herpes zoster and other viral skin infections, other infections and infestations, nonmelanoma skin neoplasms, liver function test and lipid elevations, and arterial and venous thromboembolic and thrombocytosis events. As expected given the low bioavailability and the low plasma concentrations of ruxolitinib observed following topical application, ruxolitinib 1.5% cream BID was not associated with these safety concerns.

More detailed information about the known and expected benefits and risks and reasonably expected AEs of ruxolitinib cream may be found in the IB and the prescribing information for Opzelura (Opzelura 2021).

In addition, to address challenges associated with the COVID-19 global pandemic, the sponsor has issued Protocol considerations to ensure participant safety is maintained and adequate benefit/risk analyses are applied relative to the completion of study procedures and maintaining the investigational product supply chain (see Appendix B).

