  - g. Comorbid nocturia resulting in frequent need to get out of bed to use the bathroom during the night.
  - h. Participants answering yes to all 4 of the following STOP questions from the STOP-BANG questionnaire:
    - Do you snore loudly? (Louder than talking or loud enough to be heard through closed doors)
    - Do you often feel tired, fatigued, or sleepy during the daytime?
    - Has anyone observed you stop breathing during sleep?
    - Do you have (or are you being treated for) high blood pressure?
  - i. Has clinically infected AD or has used antibiotics (systemic or topical) for their infected AD within 2 weeks prior to the screening period.
  - j. Has immune deficiency or is immunocompromised (eg, lymphoma, acquired immunodeficiency syndrome, Wiskott-Aldrich syndrome).
  - k. Has a history of skin disease or presence of skin condition that, in the opinion of the investigator, would interfere with the study assessments (eg, generalized erythroderma, Netherton syndrome, psoriasis, or any skin condition other than AD that may risk inducing a pruritus flare/worsening).
  - 1. Has had a major surgery within 8 weeks prior to screening or has a major surgery planned during the study.
  - m. Is on maintenance dialysis.
  - n. Current or history of hepatitis B virus or hepatitis C virus infection.

- 7. Has any clinically significant laboratory/vital sign abnormality that would, in the opinion of the investigator, put the participant at undue risk or interfere with interpretation of study results.
- 8. Has any of the following clinical laboratory test results at screening:
  - a. Hemoglobin < 100 g/L (ie, 10 g/dL) or ANC  $< 1000/\mu\text{L}$
  - b. Liver function tests:
    - AST or ALT  $> 2.5 \times ULN$
    - Total bilirubin > 1.5 × ULN unless Gilbert syndrome
  - c. Estimated GFR < 30 mL/min/1.73 m^2 (using the Chronic Kidney Disease Epidemiology Collaboration equation).
  - d. Positive serology test results at screening for HIV antibody.
  - e. Any other clinically significant laboratory result that, in the opinion of the investigator, poses a significant risk to the participant.
- 9. Use of any of the following treatments within the indicated washout duration prior to the pretreatment sleep assessment:
  - a. 5 half-lives or 12 weeks, whichever is longer marketed or investigational biologic agents (eg, dupilumab). For biologic agents with washout duration longer than 12 weeks (eg, rituximab), consult the medical monitor.

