triglyceride, cholesterol, or amylase)	Study drug applications must be interrupted. At the discretion of the investigator, after consultation with the sponsor, study drug application may be restored once these have resolved.			
Any Grade 4 laboratory abnormality or AST or ALT (> 20 × ULN)	Laboratory abnormalities should be confirmed with repeat testing within 48 hours whenever possible and immediate delivery of the laboratory results requested.			
	Discontinue study drug if lab abnormalities are confirmed.			

<sup>a In the opinion of the investigator.

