14.3.3 Narratives of Deaths, Other Serious, and Certain Other Significant Adverse Events			
Table 14.3.3.1	Safety	Listing of Deaths	
Table 14.3.3.2	Safety	Listing of Serious Adverse Events	
Table 14.3.3.3	Safety	Listing of Treatment-Emergent Adverse Events Leading to Discontinuation	
14.3.4 Abnormal	14.3.4 Abnormal Laboratory Values		
Table 14.3.4.1	Safety	Summary of Abnormal Laboratory Values	
14.3.5 Laborator	14.3.5 Laboratory Data Summary Tables		
Table 14.3.5.1	Safety	Summary of Clinical Chemistry	
Table 14.3.5.2	Safety	Summary of Hematology	
14.3.6 Other Safe	ety Data Summary Ta	ables	
Table 14.3.6.1	Safety	Summary of Vital Signs by Visit	

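### SAP 9.2 describes only a below/within/above-normal shift for laboratory values, which cannot register further worsening from an out-of-range baseline or separate minor from marked excursions

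*SAP*

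**What the plan says.** SAP 2.2.2 lists clinical laboratory assessments among the safety endpoints. SAP 9.2 plans three kinds of output:

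- **Continuous:** "Descriptive summaries of observed values and change from baseline will be presented for continuous hematology and chemistry for overall subjects at each study visit".
- **Categorical:** "The number of subjects with clinical laboratory values below, within, or above the normal range by time point and in relation to baseline", tabulated per analyte as a shift table.
- **Out-of-range values:** "Laboratory values that are outside the normal range will be presented via a shift table and also be flagged in the data listings", together with the normal ranges.

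The table list in SAP 13.3 adds Table 14.3.4.1, "Summary of Abnormal Laboratory Values", with no description of its rows or columns. Nothing in SAP 9.2 or the table list mentions a toxicity grade for laboratory values, a multiple of ULN, a worst post-baseline value or a count against a protocol limit. Protocol 10.4.5 plans only descriptive statistics and mean change for laboratory data.

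Three other sections matter here:

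- **Protocol 5.2, criterion 8** sets numeric exclusion limits: hemoglobin below 100 g/L, ANC below 1000/μL, AST or ALT above 2.5 × ULN, and "Total bilirubin > 1.5 × ULN unless Gilbert syndrome".
- **Protocol 6.5.1, Table 7** sets out actions for study-drug-related abnormalities at ANC below 750/μL without fever (below 1000/μL with fever), at Grade 3, at Grade 4, and at AST or ALT above 20 × ULN.
- **SAP 6.1.5** assigns early-termination and unscheduled results to analysis windows. When a window holds several results, it keeps the one nearest the target day.

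**The concern.** A three-level shift table shows movement only across a limit of normal. Someone who enters above the upper limit and rises much further has not crossed that limit again. Someone who enters within range and leaves it is counted once, however far the value goes. No output that the SAP describes therefore gives the number of participants whose laboratory values worsened to a clinically relevant degree.

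The protocol itself thinks in graded terms: Table 7 uses grades and multiples of ULN, and adverse events are graded with CTCAE v5.0. What is at stake is how well one stated safety endpoint is summarised. The primary and secondary efficacy conclusions are not affected.

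**Working it through.** The plan gives no figure to reproduce here. The check applies the SAP 9.2 rule to pairs of values that satisfy the protocol's numeric entry limits.

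**Rule.** Below if the value is under the lower limit of normal (LLN), above if it is over the ULN, otherwise within.

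**AST/ALT, in multiples of ULN (no outside figure needed)**

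| Baseline → later | Passes entry limit (≤ 2.5) | Cell | Later value > 20 × ULN |
|---|---|---|---|
| 0.8 → 21 | yes | within → above | yes |
| 1.5 → 6 | yes | above → above | no |
| 1.5 → 21 | yes | above → above | yes |
| 2.5 → 21 | yes | above → above | yes |
| 2.5 → 2.6 | yes | above → above | no |

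The last two rows share a cell. The distance from the entry limit to the Table 7 limit is 20 / 2.5 = 8-fold, all inside one category. The first row does register a shift, but it cannot be told apart from a rise to 1.1 × ULN.

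**ANC, per μL.** The documents give no LLN, so a range of 1200 to 2000 is assumed.

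| Baseline → later | Passes entry limit (≥ 1000) | Cell, at LLN 1200, 1500, 1800 and 2000 | Later value < 750 |
|---|---|---|---|
| 1000 → 740 | yes | below → below | yes |
| 1100 → 740 | yes | below → below | yes |
| 1100 → 1050 | yes | below → below | no |

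The fall from the entry limit to the Table 7 limit without fever is (1000 − 750) / 1000 = 25%, again inside one category.

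**Hemoglobin.** The same logic applies to a participant who enters below normal but at or above 100 g/L. Table 7 refers to hemoglobin by grade only, and the grade boundaries are not in the documents, so no worked figure is given.

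**Window rule (SAP 6.1.5).** The Week 4 window runs from Day 2 to Day 55 with target Day 28. A Day 2 result lies |2 − 28| = 26 days from target and a Day 55 result |55 − 28| = 27 days, so the Day 2 result would be kept and the Day 55 result left out, whichever is worse. Protocol Table 4 schedules chemistry and hematology after screening only at Week 8/EOT/ET and at safety follow-up. For these analytes the Week 4 window would therefore hold only unscheduled and early-termination samples, typically the ones drawn because something had happened.

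**The case against.** The strongest reply is that nothing is hidden.

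- SAP 4.1 includes the minimum and maximum in every continuous summary, so ALT of 21 × ULN would be seen there if its sample is the one selected for the window.
- Out-of-range values are flagged, and Listing 16.2.8.4 isolates abnormal values. SAP 6.1.5 keeps every measurement in the datasets and listings. With 47 enrolled, the listing can be read in full.
- Protocol 9.1 makes a clinically meaningful laboratory abnormality an adverse event, which then enters the severity tables.
- Exclusions 7 and 8e let the investigator turn away people whose abnormal results matter clinically, so entry is narrower than the numeric limits suggest.

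All of this stands and limits the weight of the point. The adverse event route is not a complete substitute. The last application is on the morning of the Week 8 visit, so for completers a scheduled on-treatment sample cannot lead to a change in study drug. Reporting then rests on the other criteria: clinical meaning, symptoms or need for therapy. The SAP's treatment-emergent window closes at Week 8 (EOT), while laboratory sampling continues to follow-up.

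A reader might infer four stronger claims, none of which the documents support:

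- **That the SAP departs from the protocol.** It does not. Protocol 10.4.5 asks for less than the SAP delivers.
- **That the cream has a known laboratory signal.** Protocol 2.3 says "Events of interest included cytopenias, herpes zoster and other viral skin infections" and also names liver test elevations, but these concerns come from oral treatment. The section concludes that the cream was not associated with them, and protocol 9.5 names no events of clinical interest.
- **That the three-level shift is certainly the only categorical laboratory table.** It is the only one described. Table 14.3.4.1 is most naturally that same table, but the SAP does not say so.
- **That Table 7 actions could be counted from laboratory data.** They depend on judged relatedness and, for ANC, on fever. Laboratory values and normal ranges carry neither.

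**Conclusion.** The point holds as a limit on what the planned table can show, not as a failure to report. As described, the shift table cannot register worsening in the same direction from an out-of-range baseline, merges minor and marked excursions, and under the window rule may omit the worst unscheduled or early-termination value.

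The AST/ALT result follows from the documents alone. The ANC result assumes an LLN above the participant's entry value. The 8-fold and 25% figures are distances between limits, not expected frequencies. The number of participants affected cannot be derived from the documents. Given 47 enrolled and the phase 3 experience summarised in protocol 2.3, it is probably small. This is a cheap improvement worth making, and no efficacy conclusion depends on it.

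**What to change.** Keep the existing shift table and make two additions to SAP 9.2 and the table list:

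1. **Define Table 14.3.4.1** as baseline CTCAE v5.0 grade against worst post-first-dose grade, for analytes that have grades (for example hemoglobin, neutrophils, platelets, WBC, ALT, AST, ALP and bilirubin). Use all scheduled, unscheduled, early-termination and follow-up samples, so that the nearest-to-target rule does not apply to this table. State the grade boundaries used, since neither document prints them.
2. **Add a descriptive count** of participants with any post-first-dose value crossing a purely numeric limit already in protocol Table 7: ANC below 750/μL, and AST or ALT above 20 × ULN. Label it as values crossing a limit, not as Table 7 actions.

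No clinical limit changes, and no new samples or visits are needed. The cost is SAP wording, slightly more programming and some sparse cells. The documents reviewed do not show whether the database is locked. If it is, report the table as post hoc and label it so, which SAP Section 1 allows.

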9.3. Vital Signs

Descriptive summaries of observed values and changes from baseline will be calculated for supine systolic blood pressure, supine diastolic blood pressure, heart rate, respiratory rate, and oral body temperature for overall subjects at each study visit.

9.4. Concomitant Medication

Prior and concomitant medications are defined in Section 6.1.7.1 and will be summarized descriptively using counts and percentages.

• Medications will be coded using WHODD v. MAR23B32.

9.5. Physical Exams

Whether physical exams were performed at visits will be listed.

10. Changes from Planned Analysis

- Inclusion of the ITT population
- Sponsor decision to cap enrollment at 47 subjects due to enrollment challenges.
- Exclusion of the Sufficiently Treated Population (STP) due to ePRO use challenges
- No formal statistical testing of the exploratory endpoints.

Statistical Analysis Plan, Sponsor: Incyte Corporation Protocol Number: INCB 18424-902 PCN Number: INCY 216559

11. **Other Planned Analysis**

No additional are prospectively planned for this study.

11.1. Coronavirus COVID-19

The SARS-CoV-2 virus and variants may still be a threat and safety precautions may still be in place during study enrollment. To assess the impact of the COVID-19 pandemic on study procedures, study staff will complete the COVID-19 Impact questionnaire. Should a study visit be affected by COVID-19, study staff will record how the visit was affected (missed, abbreviated, delayed, performed remotely, or otherwise deviating from the planned format in the protocol) and which procedures were impacted. All COVID-19 protocol deviations will be noted in the deviation listing.

12. References

ASA. (2018) Ethical Guidelines for Statistical Practice. Prepared by the Committee on Professional Ethics, April 2018. http://www.amstat.org/about/ethicalguidelines.cfm

ICH (1998). ICH Harmonised Tripartite Guideline. Statistical Principles for Clinical Trials E9; 1998. https://database.ich.org/sites/default/files/E9 Guideline.pdf

RSS. (2014) The Royal Statistical Society: Code of Conduct, 2014. https://rss.org.uk/about/policy-and-guidelines/code-of-conduct/.

13. Tables, Listings, and Figures

All listings, tables, and graphs will have a header showing the sponsor company name and protocol and a footer showing the file name and path, and the source of the data (e.g. listing number).

The following are planned summary tables for protocol number INCB 18424-902. The table numbers and page numbers are place holders only and will be determined when the tables are produced.

Demographic Data Summary Tables and Figures

Table 1: Demographic Data Summary Tables and Figures

Table Number	Population	Table Title/Summary
Table 14.1.1	All Subjects	Summary of Study Populations & Subject Disposition
Table 14.1.2	ITT	Summary of Important Protocol Deviations
Table 14.1.3.1	ITT	Summary of Demographics and Baseline Characteristics
Table 14.3.1.2	PP	Summary of Demographics and Baseline Characteristics
Table 14.1.4	ITT	Summary of Medical Health History

[figure not shown]

Table 14.1.5	ITT	Summary of Atopic Dermatitis and Sleep History
Table 14.1.6	ITT	Summary of Prior Medications by Therapeutic Class and Preferred Term
Table 14.1.7	ITT	Summary of Concomitant Medications by Therapeutic Class and Preferred Term

13.2. Efficacy Data

Table 2: Efficacy Data

Table Number	Population Table Title / Summary	
Table 14.2.1	PP	Summary of Mean TST Change from Baseline (Ōura Ring Data)
Table 14.2.1.1	ITT	Summary of Mean TST Change from Baseline (Ōura Ring Data) – Sensitivity Analysis
Table 14.2.2	ITT	Summary of PROMIS 8b Change from Baseline
Table 14.2.3	ITT	Summary of SOL Change from Baseline (Ōura Ring Data)
Table 14.2.4	ITT	Summary of WASO Change from Baseline (Ōura Ring Data)
Table 14.2.5	ITT	Summary of Sleep Efficiency Change from Baseline (Ōura Ring Data)
Table 14.2.6	ITT	Summary of PROMIS 8a Change from Baseline
Table 14.2.7	ITT	Summary of Itch NRS Change from Baseline
Table 14.2.8	ITT	Summary of %BSA Change from Baseline
Table 14.2.9	ITT	Summary of IGA Change from Baseline
Table 14.2.10	ITT	Summary of Light, Deep, REM (Ōura Ring Data)

13.3. Safety Data

Table 3: Safety Data

Table Number	Population	Table Title / Summary
14.3.1 Displays of Adverse Events		
Table 14.3.1.1	Safety	Incidence of Overall Treatment-Emergent Adverse Events
Table 14.3.1.2	Safety	Incidence of Treatment-Emergent Adverse Events by SOC and PT
Table 14.3.1.3	Safety	Incidence of Treatment-Emergent Adverse Events by SOC, PT, and Severity

[figure not shown]

Table Number	Population	Table Title / Summary	
Table 14.3.1.4	Safety	Incidence of Severe Treatment-Emergent Adverse Events by SOC and PT	
Table 14.3.1.5	Safety	Incidence of Treatment-Emergent Adverse Events by SOC, PT, and Relationship	
Table 14.3.1.6	Safety	Incidence of Related Treatment-Emergent Adverse Events by SOC and PT	
14.3.2 Summary of Serious and Significant Adverse Events			
Table 14.3.2.1	Safety	Summary of Serious Treatment-Emergent Adverse Events by SOC and PT	
Table 14.3.2.2	Safety	Summary of Treatment-Emergent Adverse Events Leading to Discontinuation	
14.3.3 Narratives of Deaths, Other Serious, and Certain Other Significant Adverse Events			
Table 14.3.3.1	Safety	Listing of Deaths	
Table 14.3.3.2	Safety	Listing of Serious Adverse Events	
Table 14.3.3.3	Safety	Listing of Treatment-Emergent Adverse Events Leading to Discontinuation	
14.3.4 Abnormal	14.3.4 Abnormal Laboratory Values		
Table 14.3.4.1	Safety	Summary of Abnormal Laboratory Values	
14.3.5 Laborator	14.3.5 Laboratory Data Summary Tables		
Table 14.3.5.1	Safety	Summary of Clinical Chemistry	
Table 14.3.5.2	Safety	Summary of Hematology	
14.3.6 Other Safe	ety Data Summary Ta	ables	
Table 14.3.6.1	Safety	Summary of Vital Signs by Visit	

